1.0 Objectives / Specific Aims

Machine and Human Interaction is a digital health company focused on improving patient outcomes through a virtual care platform, the Digital Wellness Nurse (DWN). The DWN uses human-in-the-loop automation, web, and mobile technology to deliver evidence-based interventions that increase a patient population's access and adherence to treatment and their engagement in healthy behaviors. The focus of the DWN for this study, in collaboration with the Medical University of South Carolina (MUSC), is to evaluate its feasibility in delivering key components of FIT Families (HL155793), a multicomponent behavioral intervention designed to treat 12-to-17-year-old African American (AA) adolescents with obesity (AAAO).

The study aims to expand the FIT Families intervention through a digital adaptation that utilizes mobile technology and automation to increase access and adherence. Specifically, the DWN platform will assist AAAOs and their primary caregivers (participants) in understanding, tracking, and completing intervention components; delivering educational content when needed; and collecting information from external sources such as wearables. An analysis of their progression will provide the participants' incentives for adhering to intervention components, for example increasing their participation in self-monitoring (SM) and physical activity (PA). The DWN enables social support (SS) by allowing additional family members or friends to offer messages of encouragement to the participants throughout the treatment. Using our web-based dashboard, community health workers (CHWs) will monitor the progress of their families, meeting with them weekly via video conference within the DWN mobile application.

DWN-FIT will evaluate the feasibility of a digital intervention to expand access and facilitate adherence to family-oriented, evidence-based treatment for AAAOs and their caregivers. Additionally, the realization of DWN-FIT will enable future research and development of evidence-based digital interventions targeting AAAOs. Successful outcomes of the proposed work will provide the evidence needed to support a larger, more comprehensive randomized clinical trial and commercialization of DWN (Phase II).

Specific Aims:

Aim 1: Feasibility Testing. Evaluate the DWN-FIT intervention (delivered by 2 CHWs) with 16 families (AAAO and caregiver, overweight or obese) undergoing treatment for adolescent obesity to determine the degree to which the DWN mobile app promotes the client's engagement in healthy behaviors, increased access to treatment for rural AA families, and improved treatment retention compared to the baseline (27% - 55% attrition). Additionally, we will determine the degree to which SS, as an additional element of DWN-FIT, enhances engagement and retention of families in the treatment.

Expected Outcome: We anticipate that healthy behaviors (increased step count, PA, nutrition SM, etc.) will be positively correlated with increased measures of engagement. Continuous engagement, we hypothesize, is highly linked to improved health outcomes, such as weight loss, which should also be reflected in measures of adherence. We also expect that SS will have a positive effect on each healthy measure, serving to increase the average step count, PA participation, and SM when compared to the non-SS condition.

Aim 2: User Centered Evaluations. Conduct a needs analysis before the intervention, a usability evaluation during the intervention and participant focus groups after the intervention to determine if the DWN app met their needs related to accessing (participants), delivering (CHWs), and providing support during the treatment.

Expected Outcome: We expect that the responses from the participants' surveys and the resulting themes will indicate that the DWN app met the participants' goals and needs related to accessing, delivering, and providing support during the treatment and was usable, efficient and effective.

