5.0 Number of Subjects

The study will include 16 African American adolescents with obesity and their overweight or obese primary caregiver for a total of 32 participants. There will also be 8 social support persons for the 8 families that are assigned to the SS condition.

The study will also include 2 community health workers.

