9.0 Study Design / Methods

Study participation will last 3 months. Families who consent to participate will be instructed to download the DWN app and complete a demographics survey. The research assistant will schedule the first session with the CHW and mail the weight scale, yoga mat, resistance bands, and Fitbit Inspire 3s to the family. Families will be randomly assigned to one of two intervention groups: the DWN-FIT or the DWN-FIT_Social Support (SS) group. CHWs will meet with families once a week for 3 months via video chat interface on the DWN-FIT app. The sessions will last approximately 45-minutes to 1 hour and will include: 1) review of SM goals; 2) review of PA steps and calories burned; 3) goal setting based on assessments and learning modules; and 4) review of CBST learning modules using evidence-based steps for skill acquisition (discussion of rationale, modeling of skill, caregiver and AAAO behavioral rehearsal of skill, feedback), and caregiver and AAAO develop implementation plans for between session skills practice.

We will also conduct a focus group with the participants after W12 of the study. These 17 focus groups (16 with participants and support person and 1 with all CHWs) will be guided by the responses to the needs analysis and usability evaluation; however, the questions will be open-ended to encourage discussions to obtain a fuller understanding of their personal experiences using the DWN. We will subsequently transcribe the audio recordings and group the data based on the discussion questions. Then, we will use either an inductive thematic analysis or a bottom-up technique to identify themes or recurring patterns in the responses. Caregivers, AAAOs, Supporters, and CHWs will be compensated \$195.55 for participating in a focus group.

Aim 1: Feasibility Testing. Evaluate the DWN-FIT intervention (delivered by 2 CHWs) with 16 families (AAAO and caregiver, overweight or obese) undergoing treatment for adolescent obesity to determine the degree to which the components of the digital intervention are correlated with adolescent-caregiver engagement in healthy behaviors and adherence to the prescribed treatment. Additionally, we will determine the degree to which SS, as an additional element of DWN-FIT, enhances engagement and retention of families within treatment.

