Methods: This aim follows two conditions (DWN-FIT vs DWN-FIT_Social Support [SS]) x 4 time (T0: baseline, T1: 1-month follow-up, T2: 2-month follow-up, and T3: 3-month end of treatment), with random assignment of 16 families (caregivers/AAAO) to one of the two treatment conditions. The proposed 3-month treatment period is too short to assess the feasibility of this digital treatment with respect to weight loss measurements (secondary outcomes), so instead we will assess feasibility of this approach based on the development of healthy behaviors (primary outcomes) that have been shown to lead to sustainable weight loss over time. Primary outcomes will be measured after each session (weekly) through the data recorded by the DWN app. These primary measures consist of the following measurements via the DWN app: step count, PA and PA video views, frequency and consistency of nutrition SM, messaging read and response rates, frequency and consistency of CBST education participation, telehealth session attendance, and CM rewards. In both treatment conditions, we will determine correlation between these measures and our measures of engagement and adherence. We will also determine the effect of semi-automated SS on each of the measures by comparing outcomes from each treatment group (DWN-FIT vs DWN-FIT_SS). Caregiver and AAAO percent

overweight and body-mass index (BMI) will serve as secondary outcome measures and will be collected each week via a provided digital scale. These secondary outcomes will be used to build preliminary data for a future full time-course (6-month or greater) randomized clinical trial (RCT).

Measures: We will measure **engagement** through the delivery of the 9-item Patient Health Engagement (PHE)⁴⁸ survey. The PHE is used to determine the degree to which patients are engaged in their own health and describes the patient's ability to manage their own health. PHE has been validated in other work, but a sample size large enough to meet this threshold is outside the scope of this study. The PHE outcomes gathered here will be used as preliminary data for future studies. The PHE survey will be taken via the DWN app at each time point, T0-T3. We will measure **adherence** through comparing the prescribed tasks against the task completed, raw counts (video views, SM entries, PA participation), by each set of participants. We will explore how SS is correlated with adherence to the prescribed treatment.

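### The protocol does not say how families are allotted to the two CHWs or that the arms are balanced by CHW, and the planned social support comparison has no CHW term

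*Protocol*

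**What the plan says.** On the providers, Aim 1 in section 1.0 of the protocol is to "Evaluate the DWN-FIT intervention (delivered by 2 CHWs) with 16 families", and section 5.0 states: "The study will also include 2 community health workers". Section 1.0 says that "community health workers (CHWs) will monitor the progress of their families, meeting with them weekly via video conference", so each CHW has a caseload. Sections 2.0 and 3.0 have the CHWs deliver Motivational Interviewing, set goals and review skills in the weekly sessions, with the option of contacting families who fall behind.

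On assignment, section 9.0 says "Families will be randomly assigned to one of two intervention groups: the DWN-FIT or the DWN-FIT_Social Support (SS) group" and, under the Aim 1 methods, "with random assignment of 16 families (caregivers/AAAO) to one of the two treatment conditions". Section 5.0 gives the arm size: "There will also be 8 social support persons for the 8 families that are assigned to the SS condition". That leaves 8 families in DWN-FIT. No block, stratum or rule for allotting families to CHWs is named.

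On analysis, the Data Analysis Strategy in section 10.0 compares the arms with an independent two-sample t-test at an alpha of 0.05. It has no term for CHW.

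**The concern.** The primary measures in section 9.0 include steps, physical activity, self-monitoring, education participation, session attendance and incentive rewards. These are the behaviours that the CHW's weekly contact is meant to move. If one CHW is more effective than the other, families will differ on these measures for a reason unrelated to SS.

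With only two CHWs, such a difference does not average out over many providers. How much of it enters the SS comparison depends on how the SS families happen to be split between the CHWs, and the protocol does nothing stated to control that split. At stake is the reading of the SS effect, which is part of Aim 1 and feeds the planning of a larger trial.

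**Working it through.** The protocol gives no power or sample-size figure to reproduce. Its counts agree: 8 + 8 = 16 families.

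**Inputs from the protocol:** 2 CHWs; 16 families; 8 per arm; two-sample t-test at 0.05.

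**Assumptions:** 8 families per CHW; one value per family; a two-sided test; a CHW difference of g within-CHW standard deviations (SD), with g from 0.25 to 1.5. None of these is in the protocol.

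**Step 1, chance of each split.** Let k be the number of SS families with CHW A. If assignment is independent of CHW, P(k) = C(8,k) × C(8,8−k) / C(16,8), with C(16,8) = 12,870.

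- 4:4: 70 × 70 / 12,870 = 38.1%
- 5:3, either way: 2 × 56 × 56 / 12,870 = 48.7%
- 6:2 or worse: (2 × 28 × 28 + 2 × 8 × 8 + 2) / 12,870 = 1,698 / 12,870 = 13.2%
- 7:1 or worse: 130 / 12,870 = 1.0%
- one CHW per arm: 2 / 12,870 = about 0.02%

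**Step 2, share carried over.** CHW A has k of the 8 SS families and 8 − k of the 8 DWN-FIT families. The CHW difference therefore enters the arm contrast with weight k/8 − (8−k)/8 = (2k−8)/8. This is 0 at 4:4, 0.25 at 5:3, 0.5 at 6:2, 0.75 at 7:1 and 1 at 8:0.

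**Step 3, unequal caseloads.** With 10 and 6 families, the weight is (2k−10)/8. It reaches one half in size at k ≤ 3 or k ≥ 7, with probability 2 × (120 × 6 + 45 × 1) / 12,870 = 1,530 / 12,870 = 11.9%. The result depends little on the caseload being exactly 8 and 8.

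**Step 4, type I error of the planned t-test** (simulation, 100,000 runs per case, no SS effect). Averaged over assignment independent of CHW, it is 4.8% to 5.1% for g from 0.25 to 1.5. For a given split:

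| Split | g = 0.5 | g = 0.8 | g = 1.0 |
|---|---|---|---|
| 4:4 | 4.4% | 3.5% | 2.9% |
| 5:3 | 4.8% | 5.0% | 4.8% |
| 6:2 | 6.8% | 9.4% | 11.5% |
| 7:1 | 10.4% | 18.0% | 25.0% |

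The first row shows that a balanced split with an unadjusted test is conservative. The CHW difference then cancels from the contrast but still inflates the residual variance.

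**Step 5, what adjustment could recover.** The correlation between arm and CHW equals the weight r in step 2. A CHW term multiplies the variance of the SS estimate by 1/(1−r²), for a given residual variance: 1.07 at 5:3, 1.33 at 6:2 and 2.29 at 7:1. At 8:0, r = 1 and the SS effect cannot be estimated apart from CHW.

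**The case against.** The strongest reply is that the protocol is silent rather than wrong. Stratification and covariates are often set out in a randomisation plan or SAP, and no SAP was available for this review. This stands in part: a reader might infer that families are randomised without regard to CHW, but no section says so. The unadjusted t-test, by contrast, is stated in the protocol itself.

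Second, if assignment is independent of CHW, the test is valid on average, and the commonest imbalance, 5:3, leaves its error rate near 5%. This also stands. A reader might infer that the planned test has an inflated type I error; step 4 does not support that. What remains is chance imbalance in the one allocation that is realised.

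Third, a reader might infer that each CHW serves one arm, so that CHW and SS are fully confounded. Nothing in the protocol indicates this. Section 3.0 gives SS families every DWN-FIT component, and independent assignment would produce that pattern only about 0.02% of the time. The protocol does not exclude it either, because CHWs could be allotted after assignment. It is the one case that no later analysis could repair.

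Fourth, CHWs share training requirements, their extra contact is optional, and prompts and incentives follow a common system. These features may make a CHW difference small, but they do not remove it. Finally, power at 8 per arm is about 32% for a true SS effect of 0.8 SD, so the comparison cannot be confirmatory in any case. That limits how much the point matters.

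**Conclusion.** The point holds as a gap in the stated design, together with an analysis that can be improved. It does not show that the comparison is biased or its test invalid. Its size is a 13% chance (12% with caseloads of 10 and 6) that at least half of any CHW difference enters the SS contrast, if assignment is independent of CHW. Short of full nesting, a CHW term can separate the two effects at some loss of precision.

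The actual size of a CHW difference is unknown; the values of g are illustrative. The change is still worth making because it is cheap and because the allotment of families to CHWs has to be settled before assignment. For a feasibility study of this size it ranks as a modest improvement.

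**What to change.** - In section 9.0, state how families are allotted to CHWs, that this is done before randomisation, and that each CHW treats families in both arms.
- Randomise in permuted blocks within CHW, giving 4 DWN-FIT and 4 SS families per CHW if caseloads are equal. The CHW contribution to the arm difference is then exactly zero.
- In section 10.0, replace the unadjusted t-test with a comparison that includes CHW as a fixed effect, because the unadjusted test would be conservative after balancing.

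The cost is two block lists instead of one, and one degree of freedom (16 − 2 = 14 falls to 16 − 3 = 13). No extra families or data are needed. If such balancing is already planned elsewhere, one sentence in section 9.0 and the CHW term in section 10.0 are enough.

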Treatment options for adolescent obesity include lifestyle modification, behavioral interventions, pharmacological treatment, and bariatric surgery (BS). However, compared to eight pharmacological options for adults, only three have been approved by the FDA for adolescent obesity, primarily because of a lack of evidence. BS is an option for adolescents with severe obesity and/or serious comorbid conditions^{13,17,18}, but there is a lack of data on its long-term safety and effectiveness^{13,17}. Further, obese children and adolescents living in rural areas are less likely to undergo an evaluation for BS¹⁹. Even with recent advances in BS and pharmacologic treatments, the first line of treatment for adolescent obesity continues to be lifestyle modifications in conjunction²⁰ with BS^{19,21,22}, medications²³, and multicomponent behavioral interventions^{24,25}. Moreover, parental involvement is also associated with the effectiveness of weight loss interventions for obese children^{26-29, 19-22}. For African American Adolescents with Obesity (AAAOs) and their family, access to intensive behavioral interventions is a challenge, especially for those living in rural areas who face limited options for healthcare providers³⁰ specializing in these interventions³¹ or inadequate transportation^{31,32}. In addition, the types of interventions for AAAO do not address the motivational factors that interfere with adherence to evidence-based recommendations. Treatment studies involving AAs have reported attrition rates ranging from 27% to 55%³³⁻³⁶. FIT Families (HL155793), the basis for the DWN-FIT, addresses access issues through an at-home evidence-based intervention and the problems with adherence and motivational factors through Motivational Interviewing (MI) delivered by Community Healthcare Workers (CHWs) and Contingency Management (CM), increasing caregiver participation by monitoring the adolescent's implementation of evidence-based cognitive behavioral skills and physical activity (PA), and modeling these skills by self-monitoring (SM) of their own diet and exercise and increasing their own PA. We propose to expand the intervention components of FIT Families by including social support (SS), which has been cited as a key element in treatment adherence³⁷⁻⁴¹ when disease management requires significant lifestyle modifications. While several studies have demonstrated a lack of moderator effects of gender on SS, we hypothesize that age (particularly children and adolescents) and race may be important moderators, a hypothesis supported by a recent review by Duh-Leong et al.⁴² who framed social support outcomes in the context of a three-component social capital construct.

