Physical Activity (PA): In W1, participants begin wearing the Fitbit wearable provided and set their step count goals during the weekly assessment. In addition, four CBST video categories will demonstrate the independent PA workouts the participants will perform weekly: 1) Warm-up (5 minutes); 2) High intensity interval training for cardiovascular fitness (20 minutes); 3) Resistance band and body weight resistance training (20 min); and 4) Cool down with yoga stretches (5 minutes). Participants will perform these PA workouts while wearing their Fitbit. The number of client workouts during the week depends on their PA goals set during the weekly assessment. The DWN provides textual and visual feedback on the client's step count and workout sessions. As a part of the PA component of the intervention, the caregiver and CHW are notified when the AAAO receives this feedback, at which time the former reviews the adolescent's progress. If the AAAO does not meet their PA goals or if the caregiver does not review the feedback, the CHW is alerted, and they have the option to reach out directly to the participants through the messaging feature. The AAAO and caregiver will receive Fitbit Inspire 3s, resistance bands, a yoga mat, and a Body Composition Scale as a part of the study. The equipment will be returned to the investigator at the end of the intervention phase.

Contingency Management (CM): The CM feature provides financial incentives to attend sessions and to encourage families to meet the following weekly goals (\$10 per goal): step count, nutrition SM, CBST education, and PA participation. Caregivers have the opportunity to receive bonus incentives (\$50 for completion over three consecutive weeks, maximum 3 bonuses over study duration) for reviewing the AAAO's PA participation and nutrition SM entries. AAAOs may also receive bonus incentives using the same pay structure (\$50) for every four consecutive weeks of at least a one-pound weight reduction. Session attendance (telehealth visit with CHW) is also incentivized at \$50 per session for the AAAO and caregiver, individually. CM

goals will be released along with the accompanying CBST material so that families have adequate knowledge to apply the prescribed strategies. Successful attendance and completion of all goals (including bonuses) over the 12-week period results in a total value of \$1230. Incentives will be disbursed as reloadable debit cards (ClinCard).

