Video Conferencing (Telehealth): Weekly telehealth sessions lasting approximately 45-minutes to 1 hour are delivered to the participants by the CHW through a video chat interface in the DWN mobile application, including 1) review of SM goals; 2) review of PA steps and calories burned; 3) Goal setting based on assessments and learning modules; and 4) review of CBST learning modules using evidence-based steps for skill acquisition (discussion of rationale, modeling of skill, caregiver and AAAO behavioral rehearsal of skill, feedback), and caregiver and AAAO develop implementation plans for between session skills practice.

DWN-FIT_Social Support (SS) intervention:

Participants randomly selected for the SS condition of the DWN-FIT will receive all of the components of the DWN-FIT intervention as described above. In addition, DWN-FIT_SS families will be asked to invite a family member/friend to serve as the supporter. Once consented and accepted as a research participant, the supporter will be compensated \$60 each week of the 12-week study period for providing encouraging messages to both the caregiver and AAAO. The supporter will be instructed by the research assistant to download the application. The supporter is automatically prompted at the following points: one day after release of CBST educational modules; twice per week for PA; and at the beginning, middle, and end of week to encourage SM and follow-up by caregivers.

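### Does calling the 27%–55% range of earlier attrition one baseline let the same retention result be reported as improved or not improved?

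*Protocol*

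**What the plan says.** Section 1.0 of the Protocol (Objectives / Specific Aims) puts retention third in Aim 1, after engagement and access: "improved treatment retention compared to the baseline (27% - 55% attrition"). The sentence is governed by "the degree to which the DWN mobile app promotes", under the label of feasibility testing. The expected outcome stated for Aim 1 concerns healthy behaviours, engagement and social support. It makes no prediction about attrition against history.

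Section 2.0 (Background) gives the source of the range: "Treatment studies involving AAs have reported attrition rates ranging from 27% to 55" percent. These are results of several earlier studies, not one rate.

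Section 5.0 fixes the size: "The study will include 16 African American adolescents with obesity and their overweight or obese primary caregiver for a total of 32 participants". The last time point in section 9.0 is "T3: 3-month end of treatment".

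Section 9.0 restates Aim 1 without the historical comparison and keeps only the effect of social support on engagement and retention. Its list of primary measures ends with "frequency and consistency of CBST education participation, telehealth session attendance, and CM rewards" and contains no retention rate. The Data Analysis Strategy in section 10.0 names Pearson correlations and a two-sample t-test between the two conditions. Neither is a comparison with past attrition.

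**The concern.** A baseline is normally one value, and here it is 28 percentage points wide. If attrition falls inside the range, an author could cite the upper end and report an improvement, or cite the lower end and report none. The choice could be made after the data are seen. A count just below the range might also be reported as a gain although 16 families cannot separate it from 27%. The study is meant to support a larger randomised trial, so a loose retention claim could carry weight later.

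**Working it through.** The Protocol states no retention threshold, power or sample-size calculation, so there is no design figure to reproduce. The check asks what 16 families can show against the range.

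**Inputs.** n = 16 families (sections 1.0 and 5.0); range 27% to 55% (sections 1.0 and 2.0). Assumptions: the family is the unit, families are independent, and a family is lost if it is not retained at T3.

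**Where the counts fall.** 0.27 × 16 = 4.32 and 0.55 × 16 = 8.80.

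| Losses | Attrition | Position |
|---|---|---|
| 4 | 25.0% | below the range |
| 5 | 31.3% | inside |
| 6 | 37.5% | inside |
| 7 | 43.8% | inside |
| 8 | 50.0% | inside |
| 9 | 56.3% | above the range |

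**Chance of a count inside the range.** With X ~ Binomial(16, p), P(5 ≤ X ≤ 8) = P(X ≤ 8) − P(X ≤ 4).

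- p = 0.27: 0.9873 − 0.5575 = 0.430
- p = 0.41 (midpoint): 0.8381 − 0.1471 = 0.691
- p = 0.55: 0.4371 − 0.0149 = 0.422

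If nothing improves on history, a count inside the range is therefore common. That is what one expects when true attrition lies in the range, and it does not show that the range misleads.

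**Chance of a count below the true value.** At p = 0.27, P(X ≤ 4) = 0.558. Compare a single comparator placed elsewhere:

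- p = 0.41: 0.41 × 16 = 6.56, and P(X ≤ 6) = 0.494
- p = 0.55: 0.55 × 16 = 8.80, and P(X ≤ 8) = 0.437

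The observed rate falls below the true rate about half the time in each case. The 0.558 reflects sampling variation and does not come from using a range.

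**Precision.** Exact (Clopper-Pearson) two-sided 95% intervals:

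| Losses | Interval | Contains |
|---|---|---|
| 0 | 0% to 20.6% | neither end |
| 1 | 0.2% to 30.2% | 27% |
| 2 | 1.6% to 38.3% | 27% |
| 3 | 4.0% to 45.6% | 27% |
| 4 | 7.3% to 52.4% | 27% |
| 5 | 11.0% to 58.7% | whole range |
| 6 | 15.2% to 64.6% | whole range |
| 7 | 19.8% to 70.1% | whole range |
| 8 | 24.7% to 75.3% | whole range |

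Only 0 losses excludes 27% on this standard. A one-sided exact test at 5% would also accept 1 loss, since P(X ≤ 1 | 0.27) = 0.045. The answer shifts with the standard chosen, and the Protocol adopts neither.

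**The case for a change.** The strongest case for a change is that the aim itself, and not some detail left for later, states its comparator in a form that gives two answers. Suppose one end were picked and tested one-sided at 5%. Beating 27% needs at most 1 loss (P = 0.045), while beating 55% allows up to 5 (P = 0.049). Counts of 2 to 5 would then pass or fail only by the choice of end. The remedy is cheap: one phrase and one interval.

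What stands is that the wording is loose and the two ends differ greatly in what they demand. The step to a defect does not stand. The 2-to-5 contrast appears only if a test is added that the Protocol does not plan. Both ends are printed in the aim, so a reader given 6 losses of 16 sees 37.5% beside 27% to 55% and places it within past experience. Calling that an improvement would mean dropping half of the stated range. The suggested rewording, to describe retention beside the range with an interval, is close to what the aim already asks.

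A further argument is that the aim credits the app, although every family also has weekly sessions with a community health worker and is paid for attending: "Session attendance (telehealth visit with CHW) is also incentivized at" $50 for each of adolescent and caregiver. That is a fair point about attribution, but it would be the same with a single comparator and does not bear on the range.

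**Conclusion.** No change is needed. It is true that a range is called a baseline and that 5 to 8 losses of 16 lie between its ends. But Aim 1 asks a descriptive feasibility question and sets no rule for success, the methods do not carry the historical comparison forward, and nothing is tested against it. Randomisation, data collection, the primary measures and the planned correlations and t-tests are untouched.

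What is left is how to present one proportion. An analyst would give the number of families retained, its uncertainty and the full historical range, and would call a count inside that range neither better nor worse than history. The SAP is not at hand and may already say so. The conclusion rests on reading improved as below the whole range, and on the family as the unit with loss judged at T3. It would be different if the Protocol made improved retention a go/no-go criterion or tested it against one chosen end. It does neither.
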